7.4.3 Summary of exploratory data

The exploratory objectives are to assess effects of mirabegron on orthostatic changes in blood pressure, depressive and anxiety symptomatology, excessive salivation, constipation and PD motor symptom severity in PD patients with OAB symptoms and CI. The related hypotheses are that mirabegron will not impact these symptoms. The goal is to demonstrate equivalent symptoms prior to and following treatment with mirabegron as well as change compared to the placebo group. Tests of equivalence will be performed using the two one-sided tests approach on change from visit 3 to visit 7 in related variables within groups as well as between the two groups. Equivalence ranges will be determined for each measure based on available literature prior to data analysis.

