1.3 Study rationale

Clinical trials of mirabegron found no central nervous system-related adverse events, such as confusion and somnolence. Its pharmacology would suggest that it has no central nervous system action, and hence should be well tolerated in patient populations vulnerable to cognitive adverse effects. This is of special interest to the PD population, because confusion, hallucinations and somnolence are common side effects among PD patients treated with anticholinergic agents (current standard of practice) for overactive bladder symptoms, although unfortunately this statement cannot be supported by clinical trials which do not exist yet constitute the experience of most experts treating PD patients. Apart from the cognitive issues, sympathetic dysfunctions are very common non-motor manifestation of PD, one of the most disruptive being orthostatic hypotension. Mirabegron is a peripheral sympathomimetic agent, and it is reasonable to assume that the use of mirabegron in PD patients may result in improved sympathetic function, conceivably lessening the burden of these symptoms.

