2. STUDY OBJECTIVES

Study objectives will focus on cognitive tolerability of mirabegron in PD patients with CI and OAB, while demonstrating efficacy in this population; exploratory analyses will look for potential positive or negative impact of the intervention on motor and non-motor aspects of PD.

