2.3 Exploratory analyses

As discussed earlier, PD has a number of non-motor symptoms resulting from peripheral sympathetic dysfunction, which could conceivably respond favorably to mirabegron. It is also of interest to ensure that mirabegron does not worsen any of the motor and non-motor symptoms of PD. Although as per protocol any worsening of these symptoms will be logged as an adverse event (AE), more specific evaluations utilizing dedicated measures will also be obtained and analyzed. Therefore, additional exploratory analyses will be performed:

- To assess the effects of mirabegron on orthostatic changes in blood pressure in PD patients with OAB symptoms and CI.
- To assess the effects of mirabegron on depressive and anxiety symptomatology, excessive salivation, and constipation in PD patients with OAB symptoms and CI.

[figure not shown]
• To assess effects of mirabegron on PD motor symptom severity in PD patients with OAB symptoms and CI.

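### Section 7.4.3 plans only equivalence tests for exploratory outcomes that the objectives want examined for benefit or harm; a between-arm difference with a 95% CI should be added

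*Combined protocol and SAP*

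**What the plan says.** Section 2 gives the general aim: "exploratory analyses will look for potential positive or negative impact of the intervention on motor and non-motor aspects of PD". Section 2.3 says that PD symptoms arising from peripheral sympathetic dysfunction are ones "which could conceivably respond favorably to mirabegron", and adds that the sponsor also wants to be sure motor and non-motor symptoms do not get worse. Section 1.3 singles out orthostatic hypotension as one of the most disruptive sympathetic problems and says the drug "may result in improved sympathetic function, conceivably lessening the burden of these symptoms".

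Section 7.4.3 covers "orthostatic changes in blood pressure, depressive and anxiety symptomatology, excessive salivation, constipation and PD motor symptom severity". Its hypothesis is: "The related hypotheses are that mirabegron will not impact these symptoms". Its method is: "Tests of equivalence will be performed using the two one-sided tests approach on change from visit 3 to visit 7 in related variables", both within and between groups. Its margins are still open: "Equivalence ranges will be determined for each measure based on available literature prior to data analysis". The statistical paragraph of the synopsis likewise names only equivalence tests for the exploratory tier.

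Two other places matter. Section 7.4.2 classes overactive-bladder symptoms as a superiority question and gives them a two-sample t-test or Mann-Whitney-Wilcoxon test. Section 7.4 asks for descriptive summaries by visit and arm (number, mean, median, SD, minimum, maximum, or counts and percentages), including change from the randomization visit.

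**The concern.** The objectives ask a two-directional question, and the analysis section asks whether nothing happened. TOST has one positive conclusion, equivalence within the margin. If it fails, the cause may be a benefit, a harm or too little information, and the verdict does not say which.

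This matters most for orthostatic pressure, where the protocol gives a mechanism for improvement and a pilot should inform the next trial. If only the planned test is reported, an improvement would appear as equivalence not shown. The plan already separates superiority from equivalence in section 7.4.2, so the distinction is familiar to its authors; it was not carried through to 7.4.3.

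**Working it through.** **Inputs from the documents.** 20 active and 10 placebo subjects (section 7.1); significance level 0.05 without multiplicity adjustment (section 7.4); TOST on change from Visit 3 to Visit 7 (section 7.4.3). There is no power figure to reproduce: section 7.1 says no formal sample size calculation was done, and no SD or margin is given for any exploratory outcome. The figures below are therefore in SD units of the change score, over assumed margins and effects, with positive meaning benefit.

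**Precision.**
- SE of the between-arm difference = SD × √(1/20 + 1/10) = 0.387 SD
- Degrees of freedom = 20 + 10 − 2 = 28
- 90% CI half-width (the interval behind TOST) = 1.701 × 0.387 = 0.66 SD
- 95% CI half-width = 2.048 × 0.387 = 0.79 SD

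**How often TOST declares equivalence** (90% CI wholly inside the margin; simulated normal data):

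| Assumed margin | No effect | 0.5 SD benefit | 0.5 SD harm | 1.0 SD benefit or harm |
|---|---|---|---|---|
| 0.5 SD | 0.2% | 0.1% | 0.1% | under 0.1% |
| 0.8 SD | 29% | 14% | 14% | 1.4% |
| 1.0 SD | 62% | 33% | 33% | 4.9% |
| 1.5 SD | 97% | 81% | 81% | 35% |

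The benefit and harm columns match for any symmetric margin. Failure does not imply an effect either: at zero difference TOST fails 99.8%, 71%, 38% and 3% of the time at these four margins.

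**The two halves of TOST separately, margin 0.8 SD.** The half that rules out worsening passes in 64% of trials at no effect, 95% at a 0.5 SD benefit and 19% at a 0.5 SD harm. It passes while the other half fails in 81% of trials at the benefit and 5% at the harm. The directional information exists, but section 7.4.3 does not ask for it to be reported.

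**What a difference with a 95% CI would add.** Two-sided 0.05 power from the noncentral t with 28 degrees of freedom is 24% at 0.5 SD, 51% at 0.8 SD and 70% at 1.0 SD; 80% power needs about 1.12 SD.

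**Can the change be computed?** Table 1 and section 3.9.3 list only UPDRS item 6 (salivation) at Visit 3. The full UPDRS is scheduled at screening and Visits 5, 7 and 8. A Visit 3-to-7 change in motor severity is therefore not available under the schedule, whichever test is used.

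**The case against.** The strongest reply has four parts.

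- *Equivalence fits a stated aim.* Section 2.3 wants assurance against worsening, and the synopsis rationale presents the drug as one that may spare constipation, orthostatic hypotension and dry mouth. A passed TOST gives that assurance up to the margin. This stands, and is why TOST should stay.
- *The test is not blind to direction.* Its two components are directional, as shown by 81% against 5%. This stands for the components, but the plan requires only the equivalence test, whose verdict merges them.
- *Direction will be visible anyway.* Section 7.4 gives change by arm, an interval can be derived from n, mean and SD, and worsening is logged as adverse events. This stands in part. No between-arm difference or interval is named, and adverse-event logging does not compare the measured scales.
- *This is a 30-subject pilot, and low pass rates partly reflect its size and the assumed margin.* True, and the added interval would not make it a confirmatory trial.

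A reader might infer that the plan expects improvement in all these outcomes and then reverses itself. The documents do not say so: section 2 is neutral on direction, section 2.3 is tentative, and the benefit rationale concerns sympathetic symptoms, with none given for depression, anxiety or motor severity. A reader might also infer that TOST should be dropped, or that the trial would yield nothing on direction. Neither follows, given the no-worsening aim and the descriptive summaries.

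**Conclusion.** The mismatch between aim and formal analysis is real and should be corrected. As written, the only formal result for each exploratory outcome is an equivalence verdict. It can rule out worsening beyond a margin, but it cannot show benefit or harm. At an assumed 0.8 SD margin the verdict is the same 14% pass rate for a 0.5 SD benefit and a 0.5 SD harm.

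The figures rest on normal data, equal variances, all 30 subjects contributing, and assumed margins. Section 7.3 excludes withdrawals, so actual intervals are likely to be wider. Salivation (one item scored 0 to 4) and constipation (six yes/no questions) fit the normal model poorly, so for them the numbers are only a guide. The symmetry argument does not depend on the SD.

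The consequence is confined to interpreting the exploratory outcomes. The primary cognitive conclusion and the overactive-bladder comparison are unaffected.

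**What to change.** 1. In section 7.4.3, report for each exploratory outcome the between-arm difference in change with its two-sided 95% CI. Read its direction against both aims: benefit, and no worsening beyond the pre-set margin. Name a suitable interval method for salivation and constipation.
2. Keep TOST as a separate question, with margins and their source fixed in advance. Note that TOST at one-sided 0.05 corresponds to the 90% CI, so reading the 95% CI against the same margin is stricter.
3. Replace the no-impact hypothesis in 7.4.3 with the two-directional aim of sections 2 and 2.3, and change the equivalence-only sentence in the synopsis to match.
4. For motor severity, name a baseline that is actually collected. Screening is the only full UPDRS before randomized treatment; Visit 5 falls two weeks into it.
5. State that these intervals are for estimation, since only effects of about 1.12 SD would be detected with 80% power.

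The cost is wording and one more interval per outcome. No new data are needed, provided the motor baseline is taken from an existing visit.

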7.4.4 Summary of safety data

Safety data and adverse events will be summarized, overall and by group, prior to each DSMB meeting and reported in the final study report.

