Descriptive statistics will be performed. The primary group for analysis will consist of all subjects who received at least one dose during the double-blind placebo-controlled phase. Analyses will compare change from randomization (visit 3) to end of treatment (visit 7). Tests of equivalence will be performed on primary, secondary and exploratory outcomes, with significance level of p<.05.

Study Procedures:

Refer to the Study Schedule/Flowchart, below.

Number of Subjects: 30 (20 active treatment, 10 placebo group).

Eligibility criteria:

INCLUSION CRITERIA:

- 1. Aged 25-80 at screening. Subjects older than 80 will be allowed at the discretion of the PI.
- 2. Ambulatory (defined as able to ambulate at least 10 meters, with or without assistance).
- 3. Clinical Diagnosis of PD based on the United Kingdom Brain Bank diagnostic criteria for PD.
- 4. At baseline visit (Visit 2) patients must have:
 - a. At least 8 micturitions per 24 hours and

- b. At least 3 urgency episodes per 3-day diary.
- 5. A MoCA score between 19 and 28 (inclusive) at screening. For those on cognitive enhancers (donepezil, rivastigmine, memantine, galantamine) a MoCA score between 19 and 29 (inclusive) at screening.
- 6. Provide informed consent to participate in the study and understand that they may withdraw their consent at any time without prejudice to their future medical care.
- 7. Be cognitively capable, in the opinion of investigator, to understand and provide such informed consent.
- 8. Be cognitively capable to complete the required questionnaires and assessments, OR have a care partner who is willing and capable to assist them in the completion of these tasks.
- 9. Be on a stable regimen of antiparkinson's medications at least 30 days prior to screening, and be expected to remain on a stable dose for the duration of the study.
- 10. If taking cognitive enhancers (donepezil, rivastigmine, memantine, galantamine), must be on stable dose at least 30 days prior to screening, and be expected to remain on a stable dose for the duration of the study.

EXCLUSION CRITERIA:

- 1. Known or suspected alcohol or substance abuse in the preceding 12 months.
- 2. Women who are pregnant or breastfeeding.
- 3. Women of childbearing potential (WOCP) who are not using at least one method of contraception.
- 4. Patients with severe renal impairment ($CL_{cr} \le 29 \text{ mL/min}$, or eGFR ≤ 29 mL/min/1.73 m²), or moderate or severe hepatic impairment (Child-Pugh classes B or C).

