3.5 Criteria for study discontinuation or early treatment termination

Study discontinuation may occur as a result of a decision from regulatory authorities, change of the opinion of the Park Nicollet Institutional Review Board (IRB), safety concerns raised by the Data and Safety Monitoring Committee (DSMC), or unavailability of the study drug.

The investigator retains the right to terminate the study at any time and for any reasons. Such study termination, however, will be subject to adequate consideration of the subjects' interests.

Individual subjects will be terminated from the study if they withdraw consent. In that instance, every effort will be made for the subject to attend an early termination visit and safety follow up.

Subjects may be withdrawn from the study at the discretion of the Investigator, for considerations relating to subject safety, or for non-adherence or loss of ability to comply with study requirements.

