6.1.8 Dose increase / Dose reduction

One scheduled dose increase will occur for the active treatment group subjects as described above at visit 5. Dose de-escalations will not be allowed prior to dose escalation (visit 5). If the subject is not tolerating study drug prior to dose escalation then the Principal Investigator will consider their withdrawal from the study. One dose de-escalation will be allowed after the dose escalation has taken place (visit 5). Thus, subjects in both treatment groups will be allowed to reduce their daily dose to 1 tablet daily, at the discretion of the Investigator. No re-escalations will be allowed due to the short duration of the study. If subjects cannot tolerate 1 tablet a day, then the Principal Investigator will consider withdrawal of the subject from the study.

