7.3 Analysis population

The analysis population is based on intent-to-treat and will consist of all participants who received at least one dose during the double-blind placebo-controlled phase. Participants who withdraw from the study or are withdrawn by the study PI will be described by screening/baseline characteristics, but excluded from analyses.

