7.4 Data summary

Data will be collected on case report forms for each participant at each visit and doubleentered into a secure study database. A quality check of data will occur after the first five records and prior to analysis, looking for out-of-range values and inconsistent data. The study statistician will conduct additional quality checks prior to data analyses including consistency between rounds of data entry, checking for duplicate entries, truncation of data, out-of-range values, inconsistent data and amount of missing data. Data discrepancies will be resolved and documented prior to data analysis. Missing data will not be imputed. After quality checks have been completed, a final database will be created with proper formatting and any appropriate mathematical algorithms applied including change from randomization visit (Visit 3).

Descriptive summaries will be generated for all demographic and clinical variables by study visit and treatment group including number, mean, median, standard deviation, minimum and maximum for continuous variables and number and percent for categorical variables. Summaries for change from randomization visit will also be generated. The number and screening/baseline characteristics of withdrawn participants will be recorded.

Subgroups for analyses may include treatment group, time point/study visit, age group and sex. A significance level of 0.05 will be used throughout with no adjustment for multiplicity. Normality will be tested throughout using the Shapiro-Wilk test. All analyses will be conducted on the final dataset in SAS version 9.3 or higher.

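### The exclusion of withdrawn participants carries no safety exemption, so read literally it takes their adverse events out of the by-group safety summary

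*Combined protocol and SAP*

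**What the plan says.** Section 7.3 calls the analysis population intent-to-treat and says it "will consist of all participants who received at least one dose during the double-blind placebo-controlled phase". The next sentence takes some of them out again: "Participants who withdraw from the study or are withdrawn by the study PI will be described by screening/baseline characteristics, but excluded from analyses". Section 7.4 adds: "The number and screening/baseline characteristics of withdrawn participants will be recorded".

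The Statistical Analysis paragraph of the synopsis gives the inclusive half without the exclusion: "The primary group for analysis will consist of all subjects who received at least one dose during the double-blind placebo-controlled phase".

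For safety, section 7.4.4 consists of one sentence: "Safety data and adverse events will be summarized, overall and by group", before each monitoring meeting and in the final study report. It names no population. No safety population is defined anywhere else in the document.

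Two sections make poor tolerability a route to withdrawal. Section 3.5: "Subjects may be withdrawn from the study at the discretion of the Investigator, for considerations relating to subject safety, or for non-adherence". Section 6.1.8: "If the subject is not tolerating study drug prior to dose escalation then the Principal Investigator will consider their withdrawal from the study". Section 6.1.8 says the same of subjects who cannot tolerate one tablet a day.

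**The concern.** A safety table is normally built on everyone who was dosed, because people who stop treatment early are often those who tolerated it badly. Here the only rule that a programmer can find removes withdrawn participants from analyses, and the safety section does not lift it. If the rule is applied to the table in 7.4.4, subjects whose adverse events led to withdrawal would not appear in it.

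The stake is limited but real. The trial's purpose is tolerability. No hypothesis test rests on the adverse-event table, but that table is the only place where adverse events are planned to be shown by arm. A subject who became confused and was withdrawn would already be out of the MoCA comparison under 7.3. On the literal reading, the by-arm adverse-event table would not show the event either.

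**Working it through.** **1. Does the exclusion reach the safety summary?**

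- 7.3 is the only population rule in section 7. Its exclusion is general and names no exception.
- 7.4 says that the number and baseline profile of withdrawn participants are recorded. It neither limits what else is recorded nor says that their events are tabulated.
- 7.4.4 neither restricts the population nor exempts safety from 7.3.
- The synopsis omits the exclusion but does not contradict it for safety.

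So the literal reading leaves these events out of the table. No sentence says the opposite.

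**2. What remains outside the table?**

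- Section 4.0 has every adverse event entered in a study log.
- Section 5.0 has the PI report adverse events to the monitoring committee.
- Section 3.9.7 asks withdrawing subjects to attend an early termination visit, where adverse events are recorded.
- Section 6.1.13 gives the blind to the statistician, and section 5.0 has the study biostatistician prepare the committee's data.

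The data and the assignments therefore both exist. What is missing is the instruction on whom to count by group.

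**3. How far could the table move?**

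The plan has no figure to reproduce: 7.1 reports no formal sample size calculation, and no withdrawal rate is stated. The inputs from the document are 20 mirabegron and 10 placebo subjects (7.1) and no replacement after randomization (7.4.6). Section 7.4.4 does not specify a statistic, so I assume the percentage of subjects with an event. Every count k below is also assumed.

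If k of n subjects have an event and one of those k is excluded, the fall is

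k/n − (k−1)/(n−1) = (n−k)/(n(n−1)).

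| n | k | All dosed | One excluded | Fall |
|---|---|---|---|---|
| 20 | 1 | 1/20 = 5.0% | 0/19 = 0.0% | 19/380 = 5.0 points |
| 20 | 6 | 6/20 = 30.0% | 5/19 = 26.3% | 14/380 = 3.7 points |
| 20 | 10 | 10/20 = 50.0% | 9/19 = 47.4% | 10/380 = 2.6 points |
| 10 | 1 | 1/10 = 10.0% | 0/9 = 0.0% | 9/90 = 10.0 points |
| 10 | 3 | 3/10 = 30.0% | 2/9 = 22.2% | 7/90 = 7.8 points |
| 10 | 5 | 5/10 = 50.0% | 4/9 = 44.4% | 5/90 = 5.6 points |

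If the excluded subject had no event, the rate rises by k/(n−1) − k/n = k/(n(n−1)). For n = 20 and k = 6 this is 6/380 = 1.6 points (30.0% to 31.6%). For n = 10 and k = 3 it is 3/90 = 3.3 points (30.0% to 33.3%).

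An event seen only in withdrawn subjects would vanish from the table: 2/20 (10.0%) would be shown as 0/18.

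**4. Is a withdrawal likely?**

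With an assumed, independent withdrawal probability d for any reason, the chance of at least one withdrawal among 20 mirabegron subjects is 1 − (1−d)^20. This is 64% at d = 5%, 88% at 10%, 96% at 15% and 99% at 20%. These are chances of any withdrawal, not of one caused by an event.

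**The case against.** The strongest reply is that 7.4.4 is the specific provision for safety and excludes nobody. It speaks of summarizing, while 7.3 speaks of analyses, and the synopsis describes analyses as comparisons of change from visit 3 to visit 7. On that view 7.3 only removes subjects who lack a visit 7 value, which fits the rule in 7.4 against imputation. Section 7.4.5 helps this reading: it rules out interim analyses, while 7.4.4 has safety summarized before each meeting, so safety summaries seem not to count as analyses.

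This is a reasonable reading, and the authors may intend it. It is not decisive. Sections 7.4.1 to 7.4.3 are also headed as summaries and contain the formal tests, so the plan does not keep the two words apart. Section 5.0 calls the committee's mid-study review an interim analysis.

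It is also fair that the route through intolerance is narrow. The synopsis keeps subjects with manageable side effects on one tablet, 6.1.8 allows one dose reduction after escalation, and withdrawal is only something the PI will consider. That lowers the likely number of affected subjects but does not settle who is counted.

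Three stronger inferences are tempting, and the documents do not support them:

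- A reader might infer that 7.4 is a second exclusion rule. It does not say that only baseline data are recorded.
- A reader might infer that this table is the only by-group look at safety. Section 7.4.1 tests cognitive tolerability between groups, 7.4.3 tests blood pressure, constipation, mood and motor measures, and 7.4 summarizes clinical variables by group. Those comparisons fall under 7.3 as well, but 7.4.4 is unique only for adverse events.
- A reader might infer that blinding of the investigators makes the by-arm split unrecoverable. The statistician holds the blind.

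**Conclusion.** The point holds in a limited form. Section 7.3 states an explicit exclusion, nothing exempts safety data, and 7.4.4 names no population. Applied literally, the by-group adverse-event table for the monitoring meetings and the final report would omit withdrawn subjects. Because the opposite reading is also open, this is wording that needs settling, and it does not show that the sponsor means to leave events out.

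The size is unknown. One omitted subject with an event costs at most 5.0 points in the mirabegron arm or 10.0 points in the placebo arm, under assumed counts and if percentages of subjects are reported. There may be no such subject. A reader might also infer a bias in favour of mirabegron. The documents do not fix a direction: the exclusion applies to both arms, and dropping a subject without an event moves the rate the other way. The events stay in the log and reach the committee, and no test depends on this table. The change should be made, since it is cheap and the subjects at issue matter most for tolerability.

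**What to change.** Add one sentence to 7.3 saying that the exclusion of withdrawn participants does not apply to safety data. Add one sentence to 7.4.4 saying that safety summaries include every subject with at least one double-blind dose, withdrawn or not, with events counted up to last contact. A by-group count of adverse events leading to withdrawal would be a useful optional line.

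Make the change before the first by-group summary is prepared for the committee. It needs no new data, visits or staff, because the events are already logged. If the sponsor already intends to count everyone dosed, the edit only puts that on record.
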